3.1.2. Part B (Multiple Ascending Dose Study)

Part B will comprise a double-blind, randomised, placebo-controlled, multiple-dose, sequential-group, escalating-dose design, enrolling healthy male subjects. Overall, 40 subjects will be studied in 4 groups (Groups B1 to B4), with each group consisting of 10 male subjects. Part B may start after completion of Group A3, at dose equal to or less than given in Groups A1 to A3.

Potential subjects will be screened to assess their eligibility to enter the study within 28 days prior to the first dose administration. Each subject will participate in 1 treatment period only and reside at the CRU from Day -1 (the day before dosing) until the morning of Day 17 (following assessments at 72 hours after final dosing).

All subjects will return for a follow-up visit 7 to 10 days after their final dose. The follow-up period may be extended depending on the observed $t_{1/2}$ of CCI [REDACTED]

In each of Groups B1 to B4, 8 subjects will receive KRP-A218 and 2 subjects will receive placebo in accordance with a randomisation schedule. The dietary state for dosing in Part B will be subject to review of the PK data from the fed/fasted comparison in Part A. For all subjects, dosing will occur on Days 1 to 14. The planned dosing frequency is once per day, however the dosing frequency in Part B may be changed following review of data from groups in Part A ([Section 3.4](#)). On Day 14, the last dose will be the morning dose regardless of the dosing frequency (QD, BID, TID).

[figure not shown]
The total daily dose administered will not exceed an exposure shown to be safe and well tolerated in Part A.

Based on the ongoing review of the safety, tolerability, and PK results, additional nonresidential visits may be required. The number of additional visits per subject will not exceed 3 and will not extend beyond 28 days after each final dosing occasion. All subjects may stay in the CRU even outside treatment period due to COVID-19 risks.

All groups in Part B will receive the IMP using a sentinel approach, as described in [Section 5.3](#). Details regarding dose escalation are presented in [Section 3.5](#).

An overview of the study design is shown in [Figure 3](#), and the planned dose levels in [Figure 5](#).

A Schedule of Assessments is presented in [Appendix 6](#).

Figure 3: Study Schematic (Part B)

The follow-up period may be extended depending on the observed $t_{1/2}$ of CCI.

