3.4. Discussion of Study Design, Including the Choice of Control Groups

For Parts A and B of the study, a sequential-group, ascending dose design has been chosen for safety reasons as KRP-A218 is in the early stages of clinical development, with Part A of the study being the first time it will be administered to humans. Oral doses have been chosen for each part of the study, as this is the intended clinical route of administration. A 2-period design has been chosen for the food-effect arm, as this gives a within subject assessment of the influence of food on the PK of **CCI** [REDACTED] and so increases the power of the study for the given number of subjects.

It is the intent of Part B to dose subjects such that steady state plasma levels of **CCI** [REDACTED] are achieved and maintained for several days. Based on the available nonclinical data, it is expected that this will be achieved following 3 days of once daily dosing; however, a full review of all the available safety, tolerability, and PK data from Part A will be performed to confirm the dose regimen for Part B. If the $t_{1/2}$ of **CCI** [REDACTED] is longer than predicted by the nonclinical data, once-daily dosing may be more appropriate over 14 days (as steady state will take longer to achieve). The dose regimen will comprise no less than once every 3 days and will not exceed 3-times daily dosing. The dosing duration will not exceed 14 consecutive days of dosing.

Details of the dosing regimen and duration used for Part B of the study will be documented in the TMF. An interval of 7 to 10 days between doses of KRP-A218 in the food-effect arm in Part A is considered adequate to prevent carryover of KRP-A218 but the interval may be extended depending on the observed $t_{1/2}$ of **CCI** [REDACTED]

Parts A and B will be double-blind and placebo-controlled in order to avoid bias in the collection and evaluation of data during its conduct. Placebo has been chosen as the control treatment to assess whether any observed effects are treatment related or simply reflect the study conditions.

Continuous 12-lead ECG monitoring will be included in this study in order to explore potential KRP-A218 effects on the QT interval, with a view of supporting a potential thorough QT study waiver.

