4.2. Part B (Multiple Ascending Dose Study)

Part B will comprise a double-blind, randomised, placebo-controlled, multiple-dose, sequential-group, escalating-dose design, enrolling healthy male subjects. Overall, 40 subjects will be studied in 4 groups (Groups B1 to B4), with each group consisting of 10 male subjects. Part B may start after completion of Group A3, at dose equal to or less than given in Groups A1 to A3.

Potential subjects will be screened to assess their eligibility to enter the study within 28 days prior to the first dose administration. Each subject will participate in 1 treatment period only and reside at the CRU from Day -1 (the day before dosing) until the morning of Day 17 (following assessments at 72 hours after final dosing).

All subjects will return for a follow-up visit 7 to 10 days after their final dose. The follow-up period may be extended depending on the observed $t_{1/2}$ of CCI

In each of Groups B1 to B4, 8 subjects will receive KRP-A218 and 2 subjects will receive placebo in accordance with a randomisation schedule. The dietary state for dosing in Part B will be subject to review of the PK data from the fed/fasted comparison in Part A. For all subjects, dosing will occur on Days 1 to 14. The planned dosing frequency is once per day, however the dosing frequency in Part B may be changed following review of data from groups in Part A. On Day 14, the last dose will be the morning dose regardless of the dosing frequency (once daily [QD], twice a day [BID], three times a day [TID]).

The total daily dose administered will not exceed an exposure shown to be safe and well tolerated in Part A.

[figure not shown]
Based on the ongoing review of the safety, tolerability, and PK results, additional nonresidential visits may be required. The number of additional visits per subject will not exceed 3 and will not extend beyond 28 days after each final dosing occasion. All subjects may stay in the CRU even outside treatment period due to COVID-19 risks.

All groups in Part B will receive the study treatment using a sentinel approach.

An overview of the study design is shown in [Figure 3](#), and the planned dose levels in [Figure 5](#).

The total duration of study participation for each subject (from screening through follow up visit) is anticipated to be up to 52 days.

Figure 3: Study Schematic (Part B)

The follow-up period may be extended depending on the observed $t_{1/2}$ of [CCI](#)

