6.2. Part B

The study treatment names and ordering to be used in the TFLs for Part B are presented in [Table 3](#).

Table 3: Presentation of Study Treatments in TFLs (Part B)

Groups	Study Treatment	Order in TFLs
B1 to B7	Placebo ^a	1
B1	XX mg KRP-A218 (QD ^b)	2
B2	XX mg KRP-A218 (QD ^b)	3
B3	XX mg KRP-A218 (QD ^b)	4
B4	XX mg KRP-A218 (QD ^b)	5
B5 ^c	XX mg KRP-A218 (QD ^b)	6
B6 ^c	XX mg KRP-A218 (QD ^b)	7
B7 ^c	XX mg KRP-A218 (QD ^b)	8

Abbreviations: QD = once daily; BID = twice a day; TID = three times a day

^a Placebo will be pooled across all groups, regardless of sex, the fasting condition, or the dosing frequency

^b The planned dosing frequency is QD, however the dosing frequency may be changed following review of data from Part A (eg, to BID or TID)

^c Optional group, to be included if required

All TFLs will be based on actual treatments (eg, if subject was assigned to receive placebo but was wrongfully dosed with active treatment they would be summarised and listed under active treatment).

All dose levels described above are the potential dose levels, and therefore are subject to change. The TFLs will reflect the dose levels utilised in the study, and these will be displayed in increasing order.

If the fasting conditions vary across groups in Part B, then the active treatment labels will include the fasting status information (eg, 'XX mg KRP-A218 (QD) (Fasted)' or 'XX mg KRP-A218 (QD) (Fed)').

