DAUC _{0-τ}	ng*h/mL/mg	area under the concentration-time curve over a dosing interval (τ) normalized by dose administered
C _{max}	ng/mL	maximum observed concentration
DC _{max}	ng/mL	maximum observed concentration normalized by dose administered
C _{min}	ng/mL	minimum observed concentration during a dosing interval
t _{max}	h	time of the maximum observed concentration
t _{1/2}	h	apparent terminal elimination half-life
CL/F	L/h	apparent total clearance
V _z /F	L	apparent volume of distribution during the terminal phase
AR _{AUC_{0-τ}}		observed accumulation ratio based on AUC _{0-τ}
AR _{C_{max}}		observed accumulation ratio based on C _{max} during the dosing interval

The dosing interval τ is 24 hours.

^a Units are based on concentration units (provided by the bioanalytical lab or preferred units for presentation of PK parameters) and dose units used in the study.

^b Area under the concentration-time curve will be calculated using the linear trapezoidal rule for increasing concentrations and the logarithmic rule for decreasing concentrations (linear up/log down rule).

Part C Day 11 (Itraconazole and Hydroxy-Itraconazole)

Parameter	Units ^a	Definition
AUC _{0-τ}	ng*h/mL	area under the concentration-time curve over a dosing interval (τ) ^b
C _{max}	ng/mL	maximum observed concentration
t _{max}	h	time of the maximum observed concentration

^a Units are based on concentration units (provided by the bioanalytical lab or preferred units for presentation of PK parameters) and dose units used in the study.

^b The AUC will be calculated using the linear trapezoidal rule for increasing concentrations and the logarithmic rule for decreasing concentrations (linear up/log down rule).

Additional PK parameters may be determined where appropriate.

The PK analysis will be carried out where possible using the actual dose of KRP-A218 administered (mg) and actual postdose blood sampling times. If an actual time is missing, the sample concentration result will be treated as missing unless there is scientific justification to include the result using the nominal time.

The parameters C_{max}, C_{min}, and t_{max} will be obtained directly from the concentration-time profiles. If C_{max} occurs at more than 1 timepoint, t_{max} will be assigned to the first occurrence of C_{max}.

The accumulation ratios (AR_{AUC0- τ} and AR_{C_{max}}) will be calculated as follows:

$$AR_{AUC0-\tau} = AUC_{0-\tau} \text{ Day 14} / AUC_{0-\tau} \text{ Day 1}$$

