- For multiple dose part of the study (Day 14), if the analyte concentration at τ (24 hours postdose) is missing, this may be substituted with the predose concentration. Similarly, if the predose concentration is missing then this may be substituted with the concentration at τ . The PK parameters from any such profile will be listed but excluded from descriptive statistics and statistical analysis.

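### SAP 8.5.1 fixes τ at 24 hours for Part B while twice- and three-times-daily dosing remain permitted; correct under the planned once-daily regimen, wrong if the change is used

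*SAP*

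**What the plan says.** Under the Part B Day 14 parameter table, SAP 8.5.1 states: "The dosing interval τ is 24 hours". SAP 8.5.1.2 identifies the τ sample as the 24-hour sample. SAP 8.5.1.3 does the same for Day 14: "if the analyte concentration at τ (24 hours postdose) is missing, this may be substituted with the predose concentration", and the reverse exchange is also allowed. ARAUC0-τ is AUC0-τ on Day 14 divided by AUC0-τ on Day 1, and ARCmax is formed in the same way.

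The frequency is not fixed. Protocol 3.1.2 says: "The planned dosing frequency is once per day, however the dosing frequency in Part B may be changed following review of data from" the Part A groups. Footnote b to SAP Table 3 (section 6.2) names twice and three times daily as examples of such a change. Protocol 3.4 sets the outer limits: "The dose regimen will comprise no less than once every 3 days and will not exceed 3-times daily dosing". On the last day, SAP 4.2 and protocol 3.1.2 agree: "On Day 14, the last dose will be the morning dose regardless of the dosing frequency".

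Neither document says what happens to τ, to the dose used for CL/F, or to the accumulation ratios if the frequency changes. The treatment labels in SAP 6.2 are the only thing that adapts.

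**The concern.** A dosing interval of 24 hours and a regimen of two or three doses a day cannot both hold. If the frequency changes and the SAP is followed literally, the Day 14 quantity labelled AUC0-τ is neither the AUC over one dosing interval nor the AUC over a full dosing day, because the later Day 14 doses are not given. The Day 1 window of the same length contains every dose of that day, so the accumulation ratio divides unlike quantities.

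AUC0-τ, Cmin, CL/F, ARAUC0-τ and ARCmax are Part B secondary endpoints. Day 14 AUC0-τ is also reported dose-normalised and enters the Part B dose-proportionality analysis (SAP 8.5.3.1).

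**Working it through.** **Inputs.** Protocol Table 3, 6 mg fasted: AUC0-∞ 1230 ng·h/mL, AUC0-24h 813 ng·h/mL, Cmax 60.3 ng/mL, median tmax 3.50 h, t1/2 16.9 h. Protocol Table 4: R = 1.6 and 1730 ng·h/mL at 8 mg.

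**The plan's own figure.** R = 1/(1 − exp(−ln2 × τ/t1/2)). With τ = 24 h and t1/2 = 16.9 h, R = 1.597, which rounds to 1.6. Then 813 × 8/6 = 1084, and 1084 × 1.597 = 1731, against 1730 stated. The figure reproduces, and it is a once-daily figure. The same formula gives 2.57 for τ = 12 h and 3.57 for τ = 8 h.

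**Direction, from linear superposition alone.** Let n be the number of doses per day.
- Day 1: each interval's AUC is at least that of the first, so AUC0-24 ≥ n × AUC0-τ.
- Day 14: with one dose and then washout, AUC0-24 lies between AUC0-τ and n × AUC0-τ.
- The 24-hour ratio therefore cannot exceed the interval ratio. The Day 14 window overstates the interval AUC and understates n times that AUC.

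**Size, under two assumed models.** Both assume linear PK, dosing at the stated frequency on Days 1 to 13, and one morning dose on Day 14. I read τ = 24 h as applying to Day 1 as well, since the ratio uses both days.
- Model 1: one compartment, AUC0-∞ 1230, t1/2 16.9 h, tmax 3.5 h (ka 0.934/h).
- Model 2: a two-compartment curve fitted to the 6 mg values, C(t) = 7309.9·exp(−0.37099t) + 44.80·exp(−0.041015t) − 7354.7·exp(−0.37581t). It returns AUC0-∞ 1226, AUC0-24h 817 and Cmax 60.2.

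| Regimen, model | Day 14 AUC0-24 / AUC0-τ | 24-h AR | Interval AR |
|---|---|---|---|
| Twice daily, 1 | 2016/1230 = 1.64 | 2016/1193 = 1.69 | 1230/444 = 2.77 |
| Twice daily, 2 | 1908/1226 = 1.56 | 1908/1361 = 1.40 | 1226/544 = 2.25 |
| Three times daily, 1 | 2824/1230 = 2.30 | 2824/1615 = 1.75 | 1230/303.4 = 4.05 |
| Three times daily, 2 | 2628/1226 = 2.14 | 2628/1867 = 1.41 | 1226/394 = 3.11 |

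Once daily, the two windows coincide and the error is zero (AR 1.64 in model 1, 1.50 in model 2). Moving t1/2 from 15.2 to 18.2 h in model 1 gives:
- twice daily: 1.55 to 1.80 against 2.56 to 2.94;
- three times daily: 1.59 to 1.87 against 3.72 to 4.31.

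**CL/F.** The SAP gives no Day 14 formula. It says only that the analysis proceeds "using the actual dose of KRP-A218 administered (mg"). Taking CL/F as dose/AUC0-24 (an inference), the result relative to the true value is:
- per-dose amount: 1/1.64 = 0.61 to 1/1.56 = 0.64 (twice daily); 1/2.30 = 0.44 to 1/2.14 = 0.47 (three times daily);
- total daily dose: 2/1.64 = 1.22 to 2/1.56 = 1.28; 3/2.30 = 1.30 to 3/2.14 = 1.40.

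**Cmin and the predose exchange.** In model 1 the Day 14 predose concentration is 1.64 times (twice daily) or 1.93 times (three times daily) the 24-hour one. A minimum taken over 24 hours is then not the trough, and the two samples are not interchangeable.

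**Dose proportionality.** If every Part B group shares one frequency, the factor is a constant on the log scale. It shifts the intercept and the dose-normalised values and leaves the slope alone. The slope is affected only if frequency differs between groups.

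**The case against.** The strongest reply is that nothing is wrong under the plan as it stands. Once daily is the planned regimen, the Part B schedule of assessments is written for it, and the observed half-life of about 15 to 18 hours is compatible with it. A change would force the schedule to be reworked anyway, and SAP section 1 requires substantial deviations to be agreed and reported. This stands, and it makes the point minor. It does not remove it, because the same SAP keeps the other regimens open and contains no rule for them.

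Point values from a one-compartment model would also be open to attack. Model 1 predicts Cmax 44 against 60.3 observed, and AUC0-24h 749 against 813. That objection stands, which is why a range is shown; the direction does not depend on the model.

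The substitution rule does little harm. SAP 8.5.1.3 lists parameters from such profiles but excludes them from descriptive statistics and statistical analysis, so the effect stops at the listings.

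A reader might infer a safety consequence: that an understated Day 14 exposure would be set against the exposure limits. The documents do not support this. Protocol 3.5 limits Part B doses by predicted steady-state exposure, and protocol 3.6 bases escalation on interim review of PK data. The SAP covers analyses for the study report, plans no interim analysis, and does not list AUC0-24h among its parameters. No safety claim is made here.

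**Conclusion.** The inconsistency is real, conditional and minor. Under once-daily dosing there is no error. If the permitted change is used, the written rule gives:
- a 24-hour accumulation ratio of about 1.4 to 1.7, against about 2.3 to 2.8 (twice daily) or 3.1 to 4.1 (three times daily);
- a Day 14 AUC about 1.6 times (twice daily) or 2.1 to 2.3 times (three times daily) the interval AUC;
- a biased CL/F under either dose convention, too low with the per-dose amount and too high with the total daily dose.

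It would go too far to quote a single CL/F error as fact, because its sign turns on a convention that the SAP does not state. The sizes rest on linear PK, a 16.9 h half-life and the two assumed curves.

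**What to change.** Replace the sentence in SAP 8.5.1 with: *τ is the dosing interval actually used in the group (24 h once daily, 12 h twice daily, 8 h three times daily). AUC0-τ, Cmin, CL/F (dose per interval divided by AUC0-τ), ARAUC0-τ, ARCmax, and the τ-sample and predose/τ substitution rules use the first such interval on both Day 1 and Day 14.* Amend the 24-hour references in SAP 8.5.1.2 and 8.5.1.3 to match.

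Alternatively, reconcile the passages by stating that Part B is once daily only and removing the other frequencies from the SAP. Which frequency to use is not a matter for this review.

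Intervals longer than 24 hours need separate treatment. Dosing every 3 days from Day 1 falls on Days 1, 4, 7, 10 and 13, so Day 14 is not a dosing day, and the profile day must be reconciled with the dosing days.

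The cost is a few lines of SAP text, best settled before unblinding and programming. No new samples are needed for 8- or 12-hour intervals. Day 14 is sampled at both times, and the 12 Day 1 samples (12 + 12 + 16 = 40, matching protocol Appendix 3) are consistent with sampling to 12 h. The sample closing the interval must be drawn before the next dose.

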8.5.1.1. Criteria for the Calculation of Apparent Terminal Elimination Rate Constant and Half-life

The start of the terminal elimination phase for each subject will be defined by visual inspection and generally will be the first point at which there is no systematic deviation from the log-linear decline in concentrations.

The apparent terminal elimination rate constant (λ_z) will only be calculated when a reliable estimate can be obtained using at least 3 data points, preferably not including C_{max} , and the adjusted coefficient for determination of exponential fit (R^2 -adj) of the regression line is ≥ 0.7 . Parameters requiring λ_z for their calculation (eg, $AUC_{0-\infty}$, $t_{1/2}$, CL/F (single dose only), V_z/F) will only be calculated if the R^2 -adj value of the regression line is ≥ 0.7 .

The following regression-related diagnostic PK parameters will be determined where possible:

Parameter	Units	Definition
λ_z	1/h	apparent terminal elimination rate constant
λ_z Upper	h	end of exponential fit
λ_z Lower	h	start of exponential fit
λ_z N		number of data points included in the log-linear regression
λ_z Span Ratio		time period over which λ_z was determined as a ratio of $t_{1/2}$
R^2 -adj		adjusted coefficient for determination of exponential fit

Where possible, the span of time used in the determination of λ_z (ie, the difference between λ_z Upper and λ_z Lower) should be ≥ 2 half-lives. If the λ_z Span Ratio is < 2 , the robustness of the $t_{1/2}$ values will be discussed in the CSR.

8.5.1.2. Criteria for Calculation and Reporting of Area Under the Concentration-time Curve

The minimum requirement for the calculation of AUC will be the inclusion of at least 3 consecutive concentrations above the lower limit of quantification. If there are only 3 consecutive concentrations, at least 1 should follow C_{max} . An exception may be made for metabolites, where C_{max} may be the last timepoint.

If the extrapolated area is $> 20\%$, $AUC_{0-\infty}$ (and derived parameters) may be excluded from the summary statistics and statistical analysis at the discretion of the sponsor or pharmacokineticist.

If $AUC_{0-\infty}$ cannot be determined reliably for all subjects and/or dose levels/treatments, an alternative AUC measure, such as AUC to a fixed timepoint or $AUC_{0-t_{last}}$, may be used in the statistical analysis of dose proportionality/food effect/sex effect.

If the τ PK blood sample is collected slightly early (i.e., the 24 hours sample), the actual sampling time of the τ sample may be used for the calculation of $AUC_{0-\tau}$. However, the $AUC_{0-\tau}$ parameter will be calculated if the τ sample is within 60 minutes of the nominal sampling time.

8.5.1.3. Criteria for Handling Concentrations Below the Limit of Quantification or Missing Concentrations for Pharmacokinetic Analysis

Plasma concentrations below the limit of quantification (BLQ) will be assigned a value of 0 before the first measurable concentration and thereafter BLQ concentrations will be treated as missing. The following rules apply to the specific situations defined below:

- If an entire concentration-time profile is BLQ, it will be excluded from PK analysis.
- Where 2 or more consecutive concentrations are BLQ at the end of a profile, the profile will be deemed to have terminated and any further quantifiable concentrations will be set to missing for the calculation of the PK parameters, unless they are considered to be a true characteristic of the profile of the drug.
- If a predose plasma concentration is missing, it will be set to 0 by default within Phoenix WinNonlin for the first dosing day of all parts of the study.
- For multiple dose part of the study (Day 14), if the analyte concentration at τ (24 hours postdose) is missing, this may be substituted with the predose concentration. Similarly, if the predose concentration is missing then this may be substituted with the concentration at τ . The PK parameters from any such profile will be listed but excluded from descriptive statistics and statistical analysis.

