8.5.1.4. Treatment of Outliers in Pharmacokinetic Analysis

If a value is considered to be anomalous due to being inconsistent with the expected PK profile, it may be appropriate to exclude the value from the PK analysis. However, the exclusion of any data must have strong justification and will be documented in the CSR.

Any quantifiable predose concentration value on the first dosing day of all parts of the study will be considered treated as 0 for the PK analysis. The PK parameters from any such profile will be listed but excluded from descriptive statistics and statistical analysis.

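### Substituting a missing Day 14 predose or 24-hour value in Part B drops every PK parameter of that profile from the statistics, including Cmax, tmax and ARCmax, which the substituted value does not affect

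*SAP*

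**What the plan says.** SAP 8.5.1.3 covers a Day 14 profile in Part B that lacks one of its two trough samples. If the sample at the end of the dosing interval is lost ("24 hours postdose) is missing, this may be substituted with the predose concentration"), the predose value may stand in for it. In the other direction, "if the predose concentration is missing then this may be substituted with the concentration at" the end of the interval. The bullet then closes: "The PK parameters from any such profile will be listed but excluded from descriptive statistics and statistical analysis".

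Four other provisions bear on this rule:

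- SAP 8.5.1 says that Cmax, Cmin and tmax "will be obtained directly from the concentration-time profiles". ARCmax is Day 14 Cmax divided by Day 1 Cmax. The same section fixes tau at 24 hours.
- SAP 8.5.1.1 says that the terminal rate constant "will only be calculated when a reliable estimate can be obtained using at least 3 data points". It does not say whether a substituted concentration may be one of them.
- SAP 8.5.1.2 handles a comparable problem by parameter. When more than 20% of the area is extrapolated, only AUC0-∞ ("and derived parameters) may be excluded from the summary statistics and statistical analysis at the discretion of the sponsor or pharmacokineticist") is at issue, and the rest of the profile stays.
- SAP 8.5.3.1 puts Day 14 Cmax, AUC0-tlast and AUC0-tau into the power model, and SAP 8.5.2 summarises all non-diagnostic PK parameters. On group size, SAP 4.2 states: "In each of Groups B1 to B4, 8 subjects will receive KRP-A218 and 2 subjects will receive placebo".

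**The concern.** The exclusion is wider than the problem it addresses. A substituted trough casts doubt only on quantities computed from that trough. The peak is observed about 3 hours after dosing and does not depend on it. Discarding the observed peak costs information in a group of eight without removing any error from Cmax, tmax or ARCmax.

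The trigger is also discretionary. Substitution is optional, and exclusion follows only when it is used. Two subjects who miss the same sample could therefore be treated differently: the one whose value is filled loses all Day 14 parameters, while the other loses none under this sentence. At stake are the Day 14 parameter summaries, both accumulation ratios (secondary endpoints) and the Day 14 dose-proportionality model.

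**Working it through.** **Inputs.** Protocol 1.3, Table 3 (6 mg fasted) gives a half-life of 16.9 h and a Cmax CV of 26.5%. Mean half-lives across the columns run from 14.8 to 18.2 h, and median tmax is 3.0 to 3.5 h. Part B Day 14 sampling is predose, 0.25 to 12 h, then 24, 36, 48 and 72 h. This fits the 40 PK samples in Protocol Appendix 3: 12 on Day 1, 12 on Days 2 to 13, and 16 from Day 14. Assumed, not in the documents: a one-compartment oral model with tmax 3.5 h, 14 once-daily doses, and a substituted value 0.70 to 1.30 times the true one.

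**Check against the protocol.** k = ln 2 / 16.9 = 0.0410 per h. R = 1/(1 − exp(−24k)) = 1.597, which agrees with R = 1.6 in Protocol Table 4.

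**Cmax and tmax.** In relative units the modelled steady-state peak is 1.351 and the trough 0.597, a ratio of about 2.3. A trough wrong by 30% cannot become the peak, so Cmax, tmax and ARCmax change by 0% in every scenario.

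**Predose substituted.** The value enters AUC0-tau only through the 0 to 0.25 h trapezoid. A 30% error gives 0.5 × 0.25 × 0.30 × 0.597 / 23.29 = 0.10%. AUC0-tlast moves by 0.06% and half-life by 0%. Cmin can be up to 30% too low.

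**24-hour value substituted.** By the log rule, the true 12 to 24 h area is 12 × (0.976 − 0.597)/ln(0.976/0.597) = 9.25. It becomes 7.89 with the value 30% too low and 10.46 with it 30% too high. As a share of 23.29, AUC0-tau changes by −5.8% to +5.2%. AUC0-tlast, which also uses the 24 to 36 h segment, changes by −6.5% to +5.9%. CL/F, Vz/F and ARAUC0-tau inherit the AUC0-tau error.

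**Half-life when the 24-hour value is substituted.** Take a regression on 24, 36, 48 and 72 h. The mean time is 45 h and the sum of squared deviations is 441 + 81 + 9 + 729 = 1260. Multiplying the 24-hour value by f changes the fitted slope by −21 × ln f / 1260.

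| f | fitted k (per h) | change in half-life |
|---|---|---|
| 0.70 | 0.0410 − 0.0059 = 0.0351 | +17% |
| 1.30 | 0.0410 + 0.0044 = 0.0454 | −9.6% |

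Without the substituted point, 36, 48 and 72 h still give the minimum of three points, and half-life does not change. They span 36/16.9 = 2.13 half-lives, or 1.98 to 2.43 for half-lives of 18.2 to 14.8 h. The SAP prefers a span of at least 2.

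**Loss of precision.** The SD on the log scale is √ln(1 + 0.265²) = 0.2605. The 95% CI factor is exp(t × 0.2605/√n).

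| n | t | factor |
|---|---|---|
| 8 | 2.365 | 1.243 |
| 7 | 2.447 | 1.272 |

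**How often.** The documents give no missing-sample rate. If each of the two samples is missing with probability p (assumed) and is always substituted, the chance that a group of eight loses at least one profile is 1 − (1 − p)^16. This is 15%, 28% and 56% for p = 1%, 2% and 5%. The figure includes profiles missing both samples, where substitution is impossible; leaving them out lowers it by at most about 1 percentage point.

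**The case against.** The strongest defence is that the rule is cautious and seldom used. Part B subjects are resident from Day −1 to Day 17, so trough samples should rarely be missed. Substitution is optional; in the modelled profile, log interpolation between 12 and 36 h recovers AUC0-tau without it. Keeping imputed profiles out of the statistics also fits the general no-imputation rule in SAP 8.1.2. Part B PK is secondary, and SAP 8.1 already advises caution because the sample size was not powered. All of this limits the size of the point. None of it explains why an observed Cmax should be dropped because a trough was filled in.

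Four stronger readings are tempting, and the documents do not support them.

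- *A reader might infer that half-life is never affected.* That is certain only when predose is the missing sample. The SAP does not bar a substituted 24-hour value from the regression, and the shift could then be +17% to −10%.
- *A reader might infer that the subject leaves all statistics.* The sentence excludes the PK parameters of that Day 14 profile. They are still listed. It does not remove observed concentrations from their summaries or touch Day 1 parameters.
- *A reader might infer that any lost trough sample costs the profile.* Exclusion follows only if the substitution is made.
- *A reader might extend the criticism to SAP 8.5.1.4*, which applies the same exclusion where "Any quantifiable predose concentration value on the first dosing day of all parts of the study will be considered treated as 0". That case differs. Protocol 4.2 excludes anyone who has previously received the study drug, so a quantifiable first-day predose value can reasonably cast doubt on the whole profile. The documents offer no basis for a tolerance threshold.

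The near-exactness of substitution also depends on once-daily dosing. The protocol allows the frequency to change. Under twice-daily dosing with a final morning dose, predose would be a 12-hour trough and not comparable with a 24-hour value.

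**Conclusion.** The point holds in a limited form. As written, SAP 8.5.1.3 discards Day 14 Cmax, tmax and ARCmax values that the substituted concentration does not affect, which is broader than the parameter-level exclusion in SAP 8.5.1.2. The cost per affected profile is 1 of 8 (12.5%) in a group's Day 14 parameter summaries and 1 of 32 (about 3%) planned active subjects in the Day 14 Cmax power model. The wider interval for a group geometric mean (factor 1.243 to 1.272) is modest and would not change the study's conclusions on its own. The 0% effect on Cmax and tmax needs only a peak well above trough. The AUC and half-life figures rest on the assumed one-compartment model, once-daily dosing and a substitution error of up to 30%.

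**What to change.** Reword the last sentence of the Day 14 bullet in SAP 8.5.1.3, for once-daily dosing with tau = 24 h, so that exclusion follows the parameter:

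- **Predose substituted:** exclude Cmin only; keep and flag the rest.
- **24-hour value substituted:** exclude Cmin, AUC0-tau, AUC0-tlast, CL/F, Vz/F and ARAUC0-tau, or show the AUC-based ones only in a flagged sensitivity summary.
- **Either case:** keep Cmax, tmax and ARCmax. State that a substituted value is never used in the terminal-slope regression. Keep half-life when it is fitted to observed points only and meets the SAP 8.5.1.1 criteria.

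If Part B moves away from once-daily dosing, the substitution rule needs restating for the new interval. No change to SAP 8.5.1.4 is called for here.

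The cost is SAP wording, best settled before unblinding, and no new data. The drawback is that n will differ between parameters within a table, which needs a footnote.
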